2.4 Protocol Amendments

This SAP incorporates the following amendments:

Table 2.4-1: Protocol Amendments

Amendment	Date of Issue	Summary of Major Changes
Revised Protocol 01 (Incorporates Amendment 03)	08-Jan-2016	The interval between the end of the combination regimen (Part 1) and the beginning of the nivolumab flat dose monotherapy (Part 2) has been amended from 3 weeks to 6 weeks. The simultaneous administration of the nivolumab and ipilimumab regimen planned in Part 1 of the treatment phase has been removed from the current protocol and will be tested in a distinct trial.
Amendment Number 05 Site Specific: All Sites in The Netherlands	13-Apr-2016	The purpose of this site-specific amendment is to add an evaluation of the PET tracer [18F]-BMS-986192 as a biomarker for PD-L1 expression in melanoma subjects, and to assess PD-L1 changes by PET following immune therapy with the combination of nivolumab and ipilimumab. This amendment impacts study conduct at CA209511 site in the Netherlands and will be implemented after IRB review and approval. This amendment does not impact study conduct at any other CA209511 sites. Up to 30 subjects will have PET scans under this amendment.
Revised Protocol 02	31-Aug-2016	To reflect updates in the nivolumab investigator brochure (IB 15):

Table 2.4-1: Protocol Amendments

Amendment	Date of Issue	Summary of Major Changes
(Incorporates Amendment 07)		
modifications were made to management algorithms (Appendix 4)
 
To reflect updates to the acceptable methods of contraception (Appendix 5).
 
Other changes were madet o resolve minor inconsistencies or to provide clarifications.

Amendment Number 08
 
Site Specific: Selected Sites in Canada, France and Spain participating in Cohort C
	28-Sep-2016	
Add Cohort C to the current CA209511 trial to investigate the overall safety and tolerability of nivolumab 6 mg/kg + ipilimumab 1 mg/kg followed 4 weeks later by nivolumab 480 mg flat dose, this regimen being repeated q8w.

3 OBJECTIVES

3.1 Primary

The primary objective is to compare the incidence of drug-related Grade 3 - 5 AEs of N3I1 to N1I3 in subjects with previously untreated, unresectable or metastatic melanoma.

3.2 Secondary

- To evaluate the ORR, as determined by investigators, of N3I1 and N1I3 in subjects with untreated, unresectable or metastatic melanoma.
- To evaluate PFS of N3I1 and N1I3 in subjects with untreated, unresectable or metastatic melanoma.
- To assess OS of N3I1 and N1I3 in subjects with untreated, unresectable or metastatic melanoma.
- To evaluate Health Related Quality of Life (HRQoL) of N3I1 and N1I3 as assessed by the European Organization for Research and Treatment of Cancer (EORTC) QLQ-C30.

[REDACTED]

4 ENDPOINTS

4.1 Primary Endpoint: Rate of Drug-related Grade 3-5 AEs

The primary endpoint of the study is the rate of drug-related Grade 3 - 5 adverse events in Arms A and B. The drug-related Grade 3 - 5 AE rate is defined as number of subjects who experienced at least 1 AE of Grade 3 or higher, judged to be related to study drug by the investigator, and with onset on or after the first dose of study treatment and within 30 days of the last dose of study treatment, divided by number of treated subjects. AE grade will be defined using National Cancer Institute Common Terminology Criteria for Adverse Events (NCI CTCAE) version 4.0 criteria.

The analysis of the primary endpoint will occur when all treated subjects who are still on-treatment have had at least 2 post-baseline tumor assessments.

4.2 Secondary Endpoints

Secondary endpoints will be analyzed at the time of the primary endpoint analysis.

4.2.1 Objective Response Rate

The first secondary endpoint is ORR in Arms A and B as determined by investigators. The ORR is defined as the number of subjects with a BOR of CR or PR divided by the number of treated subjects for each treatment group. The BOR is defined as the best response designation, as determined by the investigator, recorded between the date of randomization and the date of objectively documented progression per RECIST 1.1 or the date of subsequent anti-cancer therapy, whichever occurs first. For subjects without documented progression or subsequent therapy, all available response designations will contribute to the BOR assessment. For subjects who continue treatment beyond progression, the BOR will be determined based on response designations up to the time of initial RECIST 1.1 progression.

[figure not shown]
4.2.2 Progression Free Survival

The second secondary endpoint is PFS in Arms A and B. PFS is defined as the time from the date of randomization to the first date of documented progression, as determined by the investigator per RECIST 1.1, or death due to any cause, whichever occurs first. Clinical deterioration in the absence of progression per RECIST 1.1 is not considered progression for the purpose of determining PFS. Subjects who die without a reported progression will be considered to have progressed on the date of their death. Subjects who did not progress or die will be censored on the date of their last evaluable tumor assessment. Subjects who did not have any on study tumor assessments and did not die will be censored on their date of randomization. Subjects who started any subsequent anti-cancer therapy, including tumor directed radiotherapy and tumor directed surgery, without a prior reported progression will be censored on the date of their last evaluable tumor assessment prior to the initiation of the subsequent anti-cancer therapy.

The progression free survival rate at time T is defined as the probability that a subject has not progressed and is alive at time T following randomization.

Further explanation for various censoring scenarios for the definition of PFS are presented in [Figure 4.2.2-1](#)

Figure 4.2.2-1: Graphic Display of PFS Definition

4.2.3 Overall Survival

The third secondary endpoint is OS in Arms A and B. OS is defined as the time between the date of randomization and the date of death due to any cause. For subjects without documentation of death, OS will be censored on the last date the subject was known to be alive. The overall survival rate at time T is defined as the probability that a subject is alive at time T following randomization.

4.3.2 Safety

Overall safety and tolerability will be measured by the incidence of adverse events, serious adverse events, AEs leading to discontinuation, deaths, specific laboratory abnormalities (worst grade) and changes from baseline in each treatment group. Toxicities will be graded using the National Cancer Institute (NCI) Common Terminology Criteria for Adverse Events (CTCAE) version 4.0. See details in the Core Safety SAP¹.

4.3.3 Immunogenicity

Refer to Core Safety SAP¹.

4.3.4 Pharmacokinetics

Pharmacokinetics will be measured using serum concentration-time data of nivolumab and ipilimumab. Samples will be collected to characterize pharmacokinetics of nivolumab administered alone or in combination with ipilimumab.

4.3.5 Biomarkers

Biomarkers potentially associated with clinical endpoints will be measured by analyzing tumor and blood samples. Biomarker endpoints include, but are not limited to, single-nucleotide polymorphisms (SNPs), proteins in tumor specimens and serum, and immune cell populations.

4.3.7 ORR, PFS, and OS in Cohort C

ORR, PFS, and OS for Cohort C will be defined similarly to the other arms, except that these endpoints will be measured from the first dosing date rather than the randomization date.

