5.4.6.2 Confirmation of Scan

Verification of Response: As per RECIST 1.1, confirmation of response is required for trials with response as a primary endpoint but is no longer required in randomized studies since the control arm serves as appropriate means of interpretation of data. Hence, confirmation is NOT required.²⁷

Verification of Progression: Progression of disease should be verified in cases where progression is equivocal. If repeat scans confirm PD, then progression should be declared using the date of the initial scan. If repeat scans do not confirm PD, then the subject is considered not to have progressive disease per RECIST 1.1.

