2 STUDY DESCRIPTION

2.1 Study Design

The main study is a Phase IIIb/IV, randomized, double blind, 2-arm study of nivolumab 3 mg/kg combined with ipilimumab 1 mg/kg vs nivolumab 1 mg/kg combined with ipilimumab 3 mg/kg, in adult (≥ 18 years) subjects with previously untreated, unresectable or metastatic melanoma. Subjects must have unresectable or metastatic Stage III or stage IV melanoma, as per the AJCC staging system, and must not have received prior systemic therapy for the treatment of unresectable or metastatic melanoma.

Subjects will be randomized 1:1 and stratified by PD-L1 status and AJCC M stage as described below:

- PD-L1 expression level
 - PD-L1 $\geq 5\%$ tumor cell surface expression (in a minimum of a hundred evaluable tumor cells) vs
 - PD-L1 $< 5\%$ tumor cell surface expression (in a minimum of a hundred evaluable tumor cells)/indeterminate (tumor cell membrane scoring hampered by high cytoplasmic staining or melanin content)
- AJCC M stage at screening
 - M0/M1a/M1b vs
 - M1c

It is expected that 460 subjects will need to be enrolled in order to randomize 346 in Arms A and B, assuming a screen failure rate of 25%.

The study design schematic is presented in [Figure 2.1-1](#) and [Figure 2.1-2](#).

Figure 2.1-1: Study Design Schematic Arms A and B

[figure not shown]
[figure not shown]

Figure 2.1-2: Study Schematic for Cohort C

At selected sites, the Cohort C will be added, once the accrual in the randomized study has been completed.

This cohort (Cohort C) will be an uncontrolled and open-label single-treatment group with the same inclusion/exclusion criteria as the main CA209511 trial. The patients will be treated, in a non-randomized fashion without stratification, with nivolumab 6 mg/kg plus ipilimumab 1 mg/kg followed by nivolumab 480 mg Flat Dose 4 weeks later and repeated every 8 weeks. M-staging, PDL-1 status and BRAF status must be collected in eCRF but is not mandated prior to treatment.

At activation of this amendment at selected sites, approximately 25 subjects will be treated by a combination dose and schedule of nivolumab plus ipilimumab (Cohort C). This amendment impacts study conduct at CA209511 selected sites in selected countries. This amendment does not impact study conduct at any other CA209511 sites.

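### Cohort C takes over the unconfirmed response definition although the protocol's argument for waiving confirmation (randomization, a control arm) does not apply to it; label that ORR as unconfirmed and add a confirmed ORR

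*SAP*

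**What the plan says.** **Response definition, Arms A and B.** SAP 4.2.1: "The BOR is defined as the best response designation, as determined by the investigator", up to RECIST progression or subsequent therapy. ORR is the share of treated subjects whose BOR is CR or PR. Neither definition contains a confirmation step.

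**Why there is none.** Protocol 5.4.6.2, citing RECIST 1.1, makes confirmation mandatory where a trial's primary endpoint is response. It then gives a waiver with its reason, that the step is "no longer required in randomized studies since the control arm serves as appropriate means of interpretation of data". From this it draws the conclusion that the present study needs no confirmation.

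**Cohort C.** SAP 4.3.7: "ORR, PFS, and OS for Cohort C will be defined similarly to the other arms". The one exception it names is that time runs from first dose instead of randomization. SAP 2.1: "This cohort (Cohort C) will be an uncontrolled and open-label single-treatment group". The same section says that its subjects are neither randomized nor stratified. SAP Section 5 puts it at about 25 treated subjects, calls it exploratory, and plans a descriptive evaluation in a separate report. SAP Table 2.4-1 gives the purpose of Amendment 08, which added the cohort, as safety and tolerability.

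Neither document plans a confirmed ORR for Cohort C or says that its ORR will be labelled as unconfirmed. The protocol reviewed does not mention Cohort C, and the text of Amendment 08 was not available.

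**The concern.** The protocol's argument for accepting a single qualifying scan is that a control arm makes the rate interpretable: chance threshold crossings occur in both arms and largely cancel in the comparison. Cohort C has no control arm. SAP 4.3.7 did adapt the endpoints to a cohort without a randomization date, but it left unchanged the one response rule whose stated justification also depends on randomization.

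Without a concurrent comparator, the ORR of Cohort C will be read as an absolute level of activity for a new regimen. Three features allow single-scan responses to raise it:

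- The investigator reads the scans and knows the treatment.
- Images are stored only for possible later central reading (Protocol 5.4 and 5.4.2).
- BOR takes the best of several scans, so every further scan before progression is another chance to cross the 30% line.

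What is at stake is how one descriptive result is read. No test or decision rule depends on it.

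**Working it through.** **1. The plan's own figure.** The documents state no ORR figure for Cohort C. The exact-interval method can be checked on SAP Table 5-1: Clopper-Pearson for 102/170 gives 52.2% to 67.4%, as printed.

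**2. Does the waiver carry over?**

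| Element of Protocol 5.4.6.2 | Arms A and B | Cohort C |
|---|---|---|
| Response is the primary endpoint (confirmation required) | No | No (exploratory; safety and tolerability) |
| Randomized with a control arm (confirmation waived) | Yes | No |

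Cohort C falls under neither limb: the text does not demand confirmation, and its reason for waiving it is absent.

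**3. Direction and unit.** Every confirmed response is also an unconfirmed one, so confirmed ORR ≤ unconfirmed ORR. With n = 25, each response that is not confirmed moves the rate by 1/25 = 4 points.

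**4. Possible size.** The documents give no confirmation rate. Assume 15 of 25 unconfirmed responses (60%, the rate used as an illustration in SAP Section 5), with k of them not confirmed. Confirmed ORR = (15 − k)/25.

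| k | Confirmed ORR | Exact 95% CI | Gap |
|---|---|---|---|
| 0 | 60% | 38.7% to 78.9% | 0 |
| 1 | 56% | 34.9% to 75.6% | 4 points |
| 2 | 52% | 31.3% to 72.2% | 8 points |
| 3 | 48% | 27.8% to 68.7% | 12 points |
| 4 | 44% | 24.4% to 65.1% | 16 points |

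The last row is a non-confirmation share of 4/15, about 27%. The interval at 15/25 is 78.9 − 38.7 = 40.2 points wide, more than any gap in the table.

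**5. Error in both directions.** Illustration; every input is assumed. Measured change = true change + independent normal error, SD 5 to 10 percentage points, 3 to 5 scans, and 5 of the 25 subjects of the type considered. Let p be the chance that one scan shows a decrease of at least 30%, q = 1 − p, and m the number of scans.

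- At least one qualifying scan (unconfirmed): 1 − q^m
- At least two qualifying scans (met again later): 1 − q^m − m·p·q^(m−1)

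*Subject with a true, stable 20% shrinkage (not a responder).* p = Φ(−2) = 0.0228 at SD 5 and Φ(−1) = 0.1587 at SD 10.

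- Counted without confirmation: from 1 − 0.9772³ = 6.7% to 1 − 0.8413⁵ = 57.8%. Times 5/25, this adds 1.3 to 11.6 points.
- Counted with confirmation at any later scan: 0.15% (SD 5, 3 scans) to 18.1% (SD 10, 5 scans), adding 0.0 to 3.6 points. If the two scans must be consecutive: 0.1% to 8.8%, adding 0.0 to 1.8 points.

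*Subject with a true, stable 35% shrinkage (a responder).* p = Φ(1) = 0.8413 at SD 5 and Φ(0.5) = 0.6915 at SD 10.

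- Missed by the confirmed rate, any later scan: q^m + m·p·q^(m−1) = 0.3% (SD 5, 5 scans) to 22.7% (SD 10, 3 scans), removing 0.1 to 4.5 points.
- Missed if the two scans must be consecutive: 3.5% to 37.4%, removing 0.7 to 7.5 points.

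Confirmation therefore removes most chance responders but also loses some true ones. Independent errors are a simplification, because every change from baseline shares one baseline measurement.

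**The case against.** **The protocol sentence has two halves.** A reader might infer that confirmation was dropped only because a control arm exists, so that Cohort C breaches the protocol's own rule. The documents do not support that: the same sentence ties the requirement to response as a primary endpoint, which it is not in Cohort C. This objection stands. What remains is that the stated reason for the waiver is missing and nothing replaces it.

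**The rate is not shown to be biased.** A reader might infer that the Cohort C ORR is biased upward. It estimates the quantity that the SAP defines. It misleads only if read as a confirmed rate, and the gap could be zero. This stands too: the difference is one of definition, in one known direction.

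**Amendment 08 may settle it.** It was not available, and a definition that is only similar leaves room for a rule of its own. That is a reason to cite the rule in SAP 4.3.7, where only the time origin is named as an exception.

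**Replacing the headline rate would do harm.** It would break the shared definition with Arms A and B, drop responders whose next scan is missed, and lose true responders to measurement error. Nor does a second reading by the same unblinded investigator remove open-label reader bias. All of this stands and argues for showing both rates.

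**Durability is visible elsewhere.** SAP 7.5.1 plans duration of response, responder time courses and waterfall plots by treatment group, and does not limit them to Arms A and B. These help a careful reader, but they do not give a confirmed rate with an interval.

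**The interval is wide anyway.** True, at about 40 points. But it expresses sampling error and does not correct a shift that goes one way.

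**Conclusion.** The point holds as a minor one. Cohort C's ORR counts unconfirmed responses under a waiver whose stated justification does not fit an uncontrolled, open-label cohort, and the SAP plans neither a label nor a confirmed rate beside it. The unconfirmed rate can only equal or exceed the confirmed one, at 4 points per response that is not confirmed.

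The documents do not determine the size of the gap. The 0 to 16 points above rest on an assumed 60% unconfirmed ORR with up to 4 of 15 responses failing; the measurement-error figures rest wholly on assumed inputs. Neither a breach of the protocol nor a demonstrated upward bias is established. The cohort is exploratory and descriptive, and the Arms A and B analyses are untouched. The conclusion assumes that Amendment 08 contains no confirmation rule of its own.

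**What to change.** In SAP 4.3.7:

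1. Keep the ORR as defined, for consistency with Arms A and B, and label it as unconfirmed wherever Cohort C is reported.
2. Add a confirmed ORR for Cohort C: CR or PR counts if the criteria are met again at a subsequent scheduled tumor assessment. Give its Clopper-Pearson 95% CI and show both rates together. State how a missed or non-evaluable scan in between is handled, and report the number of responders still awaiting a later scan at the data cut-off.
3. If Amendment 08 already sets a rule, cite it instead.
4. If the confirmed rate is ever set beside Arms A and B, derive theirs in the same way.

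**Cost:** a sentence or two in the SAP and one extra derivation. No new scans are needed, provided that Cohort C is scanned at least as often as the main study, which the available documents do not show.

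**Downside:** responders first seen at the last scan before the cut-off are pending, and some true responders will fail confirmation through measurement error or a missed scan. That is why the confirmed rate should accompany the unconfirmed one and not replace it.

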5 SAMPLE SIZE AND POWER

Approximately 346 subjects will be randomized to the 2 treatment arms A and B in a 1:1 ratio in order to target 340 treated subjects (170 per arm). Given a two-sided alpha of 0.05, this number of treated subjects provides 80% power to show a statistically significant difference in the rate of drug-related Grade 3 - 5 AEs between the two treatment arms, assuming a rate of 40% in Arm A and a rate of 55% in Arm B.

We assume that treatment with N3I1 (Arm A) will result in a 15% reduction in the rate of drug-related Grade 3 - 5 events when compared to treatment with N1I3 (Arm B). The difference of 15% is clinically meaningful and assumes a 40% event rate in Arm A and a 55% event rate in Arm B. The assumption of 55% in Arm B is based on observed rates of drug-related Grade 3 - 5 AEs in the combination arm of studies CA209069 and CA209067, which enrolled the same patient population as the current study (previously untreated metastatic melanoma). The assumed reduction to 40% in Arm A corresponds to the same rate ratio (0.727) that was observed in Cohort 2a relative to Cohort 2 in Study CA209004.

Table 8.1-1 shows the precision that the sample size of 170 treated subjects per arm will provide for estimating adverse event rates (primary endpoint) or objective response rates (secondary endpoint), under different assumed observed rates.

For example, if exactly 68 of 170 treated subjects (40%) experience a drug-related Grade 3 - 5 AE in Arm A and 94 of 170 treated subjects (55.3%) experience a drug-related Grade 3 - 5 AE in Arm B, then the exact 95% CI for the rate of drug-related Grade 3 - 5 AEs will be (32.6%, 47.8%) for Arm A and (47.5%, 62.9%) for Arm B.

Furthermore, if exactly 102 of 170 treated subjects (60%) experience an objective response in a treatment arm, then the exact 95% CI for the ORR in that treatment arm will be (52.2%, 67.4%). If the observed ORR is exactly the same in each arm and equal to 60%, then the 95% CI for the difference in ORR between arms will be (-10.4%, 10.4%), and the 95% CI for the odds ratio will be (0.65, 1.54).

Table 5-1: Exact 95% CI for Rates when Observed in 170 Subjects

Number Subjects with Event	Observed Rate	Lower limit Exact 95% CI	Upper limit Exact 95% CI
68	40.0%	32.6%	47.8%
77	45.3%	37.7%	53.1%
85	50.0%	42.2%	57.8%
94	55.3%	47.5%	62.9%
102	60.0%	52.2%	67.4%

Following completion of enrollment into Arm A and Arm B of the main study, approximately 25 additional subjects will be treated in an independent Cohort C for purposes of an exploratory sub-study. Subjects in Cohort C will not be included in the primary analysis and will be evaluated descriptively in a separate report.

Thus the total number of subjects expected to be treated in the CA209511 study is 365, consisting of 340 treated in the randomized double-blind main study and 25 treated in the open label exploratory sub-study (Cohort C).

6 STUDY PERIODS, TREATMENT REGIMENS AND POPULATIONS FOR ANALYSES

6.1 Study Periods

6.1.1 Baseline Period

Study Baseline

Baseline evaluations or events will be defined as evaluations or events that occur before the date and time of the first dose of study treatment. Evaluations on the same date and time of the first dose of study treatment will be considered as baseline evaluations.

In cases where the time (onset time of event or evaluation time and dosing time) is missing or not collected, the following definitions will apply:

- Pre-treatment AEs will be defined as AEs with an onset date prior to but not including the day of the first dose of study treatment
- Baseline evaluations (laboratory tests, pulse oximetry and vital signs) will be defined as evaluations with a date on or prior to the day of first dose of study treatment

If there are multiple valid assessments, the assessment that is closest to day (and time if collected) of the first dose of study treatment will be used as the baseline in the analyses. If multiple assessments are collected at the same date (and time if collected), the assessment with the latest database entry date (and time if collected) will be considered as baseline.

If more than one tumor biopsy specimen is available, baseline PD-L1 expression will be determined from the most recently collected specimen (prior to first dose of study treatment) with a measurable result. If all specimens for a given subject are either indeterminate or unknown, then the PD-L1 expression will be considered indeterminate as long as at least one specimen is indeterminate. Otherwise, PD-L1 expression will be considered unknown.

Baseline for Part 2 Treatment Period

Baseline evaluations or events for the Part 2 Treatment Period will be defined as evaluations or events that occur before the date and time of the first dose of Part 2 study treatment. Evaluations on the same date and time of the first dose of Part 2 study treatment will be considered as baseline evaluations. Conventions for handling missing or not collected time and multiple assessments will be as described above except that the Part 2 dosing date will replace the study dosing date.

